### 7.2 Advice on the Risks of Smoking/Smoking Cessation Advice and Debriefing on IQOS

All patients included in the study will be first advised that the best ways of preventing further periodontal disease progression is to stop smoking as defined in the Japanese guidelines for periodontitis [78]. Only patients who are not willing to quit smoking cigarettes will be eligible for the study.

From V1 onwards, information on the risks of smoking and advice to quit smoking will be given to all patients at every Visit. This will take the form of a brief interview according to WHO recommendations [97].

In addition to the information of the risk of use of tobacco-containing products on smoking products/smoking cessation advice, a debriefing of patients will be done at each visit to address any intended or unintended beliefs participants have about IQOS. The goal of the debriefing is to ensure that patients have an accurate understanding of product risks including an understanding that IQOS has not been demonstrated to be less harmful than cigarettes.

#### Confidentiality Statement

---

Data and information contained in this document are considered to constitute trade secrets and confidential commercial information, and the legal protections provided to such trade secrets and confidential information are hereby claimed under the applicable provisions of applicable law. No part of this document may be publicly disclosed without the written consent of Philip Morris Products S.A.

---

Any enrolled patient, who is willing to attempt quitting during the study will be encouraged to do so and will be referred to appropriate medical services. The patients who quit smoking or using IQOS or those who quit smoking and start using IQOS will not be discontinued from the study, will receive their financial compensation and will come at all scheduled visits for assessments.

### 7.3 Dental/Clinical Assessments

As per medical responsibility plan, a medical expert (dentist) will be the primary contact for dental medical questions that Investigators might have. Dental medical monitors will be the co-primary contacts for dental medical questions. Other roles for medical expert and dental medical monitors are defined in the medical responsibility plan.

#### 7.3.1 Demographic Data

Demographic data (sex, date of birth, ethnicity) will be recorded at V1.

#### 7.3.2 Questions on Smoking History/Habits and Intention to Quit Smoking

Patients will be questioned for their smoking history and self-reported current tobacco and nicotine containing tobacco product use over the past month at V1. The patient will also be asked if he/she is planning to quit smoking during the study. This information will be used to assess their eligibility for the study.

#### 7.3.3 Presentation of IQOS

IQOS including *HeatSticks* will be presented to all male patients by the Investigator or study collaborator at V1. With respect to female patients, it will be presented to the patients whose pregnancy test was negative.

#### 7.3.4 Dental/Medical History and Previous and Ongoing Medications

Relevant dental/medical history and any concomitant disease will be documented at V1. Dental/medical history is defined as any condition that started and ended prior to ICF signature. A concomitant disease is defined as any condition that started prior to ICF signature and is still ongoing at the end of V1.

Prior medication taken within 3 months prior to screening and any ongoing medication at screening needs to be documented. Any medication which is started prior to screening and is still being taken by the patient at screening or thereafter will be considered as concomitant medication. This applies to both prescription and over-the-counter products.

#### Confidentiality Statement

---

Data and information contained in this document are considered to constitute trade secrets and confidential commercial information, and the legal protections provided to such trade secrets and confidential information are hereby claimed under the applicable provisions of applicable law. No part of this document may be publicly disclosed without the written consent of Philip Morris Products S.A.

---

If the use of a concomitant medication cannot be avoided for the patient's safety, it must be fully documented in the Source Document and CRF. Therapy changes (including changes of regimen) during the study have to be documented.

### 7.3.5 Dental Assessments

In the investigational sites with two or more dentists, a dentist will measure each periodontal disease parameter. In the investigational sites with one dentist only, a dentist will preferably measure these parameters, however, a trained hygienist could also do it.

From the moment the examiner meets the patient, blinding of the smoking status should be ensured, as described in section 6.4.1.

A single examiner at each site will perform all measurements throughout the whole study duration, if possible. A calibration session between examiners from different sites must be organized before V1.

Each site will need to develop a plan on how to ensure that they have properly qualified personnel, including back-up personnel necessary to conduct the required dental assessments. This will be documented in the delegation of authority log.

Unified periodontal probes will be used to ensure that all examiners will apply the same pressure when probing. The probe in this study will be PCPUNC15 (#30) by Hu-Friedy. Measurements will be rounded to the nearest millimeter (mm), based on visual judgement.

The dental assessments listed in the sections 7.3.5.1 to 7.3.5.8 below will be recorded on the prescribed periodontal charts.

#### 7.3.5.1 Target Tooth

At V1, for all eligible patients, the Investigator or designee will designate 4 target teeth, *i.e.*, preferably one per quadrant. Teeth with PD  $\geq 5$  mm but  $< 7$  mm will be preferably selected. If their location does not correspond to one per quadrant, the Investigator or designee will designate the target teeth preferably as single-rooted, and distributed as evenly as possible. Target teeth identification will be reported in the CRF.

#### 7.3.5.2 Target site

The Investigator or designee will designate one site on each target tooth (section 7.3.5.1), which will be the target sites for GCF collection (section 7.5.3). These four target sites should preferably be the deepest of the target teeth. Target site identification will be reported in the CRF.

### 7.3.5.3 Pocket Depth (PD)

PD is the distance from the gingival margin to which a probe penetrates into the pocket. Full mouth PD is measured based on 6 sites per tooth (6-site measurement method) at a pressure of approximately 20g using the intended probe at V1, V3 and V4. PD is recorded in 1 mm increments. If PD is not measurable on more than 2 sites, the whole tooth should be skipped and any periodontal parameters will not be measured for the tooth.

The site must differentiate within their documentation when PD is not measured from when PD cannot be measured as there is no longer a pocket to measure.

For each subject, full mouth PD is calculated by the following formula:

$$\text{Full Mouth PD (mm)} = \frac{1}{t} \sum_{i=1}^t \sum_{j=1}^{s_i} \frac{PD_{ij}}{s_i}$$

where  $PD_{ij}$  is the PD measurement of tooth  $i$ ,  $i = 1, \dots, t$  at the site  $j$  where  $j = 1, \dots, s_i$ . Note that  $s_i$  is the number of measurable sites per tooth and  $s_i \geq 4$ .

### 7.3.5.4 Clinical Attachment Level (CAL)

CAL is the measured distance from an invariable reference point such as CEJ to the bottom of pocket using the intended probe based on 6 sites per tooth (6-site measurement method) in full mouth at V1, V3 and V4. CAL is recorded in 1 mm increments. If CAL is not measurable on 1 or 2 of 6 sites on V1, the site(s) should be skipped but the tooth can be included in the assessment. If CAL is not measurable on more than 2 sites, the whole tooth should be skipped. If the CEJ is unclear on site(s), the fixed point (e.g. margin of the crown) will be chosen if possible and distance from the chosen fixed point to the bottom of pocket will be measured, and the same position will be measured throughout the study period. The site must differentiate within their documentation when CAL is not measured from when CAL cannot be measured as there is no longer attachment loss to be measured.

For each subject, the mean Full mouth CAL is calculated by the following formula:

$$\text{Full Mouth CAL (mm)} = \frac{1}{t} \sum_{i=1}^t \sum_{j=1}^{s_i} \frac{CAL_{ij}}{s_i}$$

Where  $CAL_{ij}$  is the CAL measurement of tooth  $i$ ,  $i = 1, \dots, t$  at the site  $j$  where  $j = 1, \dots, s_i$ . Note that  $s_i$  is the number of measurable sites per tooth and  $s_i \geq 4$ .

### 7.3.5.5 Bleeding on Probing (BOP)

BOP in full mouth is determined to assess inflammatory status in the pocket and is assessed as YES or NO of bleeding at 6 sites per tooth at V1, V3 and V4. Gently probing (approximately 20g pressure), the bleeding site within 30 seconds is assessed as YES. For each subject, BOP is calculated by the following formula:

$$\text{Full Mouth BOP (\%)} = 100 * \frac{1}{t} \sum_{i=1}^t \sum_{j=1}^{s_i} \frac{BOP_{ij}}{s_i}$$

Where  $BOP_{ij}$  is a binary response (Yes = 1, No = 0) of bleeding of tooth  $i$ ,  $i = 1, \dots, t$  at the site  $j$  where  $j = 1, \dots, s_i$ .

### 7.3.5.6 Tooth Mobility

Tooth mobility will be assessed by Miller's classification [19] below to observe periodontal severity in full mouth at V1, V3 and V4:

Grade 0: Physiologic movement within 0.2 mm

Grade 1: Slight mobility, tooth can be moved 0.2 – 1 mm labiolingually

Grade 2: Moderate mobility, tooth can be moved 1 – 2 mm labiolingually or mesiodistally

Grade 3: Severe mobility, tooth can be moved more than 2 mm labiolingually or mesiodistally, or ability to depress the tooth in a vertical direction

### 7.3.5.7 Gingival Index (GI)

The degree of gingival inflammation of the target teeth is assessed by calculating the GI of each target tooth. Six surfaces of each tooth of the target teeth are rated according to the score by Löe and Silness [36]. The surfaces are rated according to the following criteria:

Score Criteria:

0: Normal gingiva.

1: Mild inflammation – slight change in color, slight edema, no bleeding on probing.

2: Moderate inflammation – redness, edema and glazing, bleeding on probing.

3: Severe inflammation – marked redness and edema, ulceration, tendency to spontaneous bleeding.

For each subject, GI of target teeth is calculated by the following formula:

### Confidentiality Statement

Data and information contained in this document are considered to constitute trade secrets and confidential commercial information, and the legal protections provided to such trade secrets and confidential information are hereby claimed under the applicable provisions of applicable law. No part of this document may be publicly disclosed without the written consent of Philip Morris Products S.A.

$$GI = \frac{1}{t} \sum_{i=1}^t \sum_{j=1}^{s_i} \frac{GI_{ij}}{s_i}$$

where  $GI_{ij}$  is the GI of target tooth  $i$ ,  $i = 1, \dots, t$  at surface  $j$  where  $j = 1, \dots, s_i$ .

#### 7.3.5.8 Plaque Control Record (PCR)

Presence of the plaque on individual tooth surfaces in full mouth is assessed and PCR (%) is calculated.

According to the PCR of O'Leary et al. [20], plaque retention in the dentogingival areas of mesial, distal, facial and lingual tooth surfaces is determined to be YES or NO and recorded at V1, V3 and V4.

Usual plaque disclosing agent is used in each site and the product name of the plaque disclosing agent will be recorded.

For each subject, PCR (%) is calculated by the following formula:

$$Full\ Mouth\ PCR\ (\%) = 100 * \frac{1}{t} \sum_{i=1}^t \sum_{j=1}^{s_i} \frac{PCR_{ij}}{s_i}$$

Where  $PCR_{ij}$  is a binary response (Yes = 1, No = 0) of PCR at tooth  $i$ ,  $i = 1, \dots, t$  at the surface  $j$  where  $j = 1, \dots, s_i$ .

## 7.4 Biomarker Assessments

### 7.4.1 Assessments in Urine

All bioanalytical assays will be carried out using validated methods (section 7.5.6). The bioanalytical methods used will be documented in the Bioanalytical Plans/Reports. A list of laboratories is provided in Appendix 2.

#### 7.4.1.1 NEQ, total NNAL, CEMA, Creatinine Analysis

Spot urine will be collected at V1, V3 and V4 for analysis of NEQ, total NNAL, a biomarker for NNK (*i.e.*, nicotine-derived nitrosamine ketone, also known as 4-(methylnitrosamino)-1-(3-pyridyl)-1-butanone), CEMA, a biomarker for acrylonitrile, and creatinine. Creatinine will be measured for normalization of urinary BoExp, *i.e.*, NEQ, total NNAL and CEMA.

## 7.5 Other Clinical Assessments and Sampling

Sample collection of GCF, SP and buccal swabs will be performed prior to periodontal assessment, scaling/maintenance or scaling and root planing (SRP).

From V2 to V4, patients will be asked not to drink, eat, chew gum, use mouth rinse or brush their teeth for at least 30 minutes before collection of oral samples (*i.e.*, SP, GCF or buccal swabs).

### 7.5.1 Urine Pregnancy Testing

All female patients will undergo urine pregnancy testing at all Visits.

Female patients with a urine positive pregnancy test at the V1 cannot be enrolled and will be considered a screening failure. In any case of a positive urine pregnancy test, the Investigator will inform the patient about the risks associated with smoking during pregnancy.

All pregnancies detected during the study must be reported and handled as described in Section 8.5.

### 7.5.2 Cotinine Test

A urine cotinine test will be performed at V1 in order to confirm the patient's smoking status. The test must detect cotinine with a cotinine of  $\geq 200$  ng/mL (*e.g.*, One-Step Cotinine Test 008A086, Ultimed, Belgium).

### 7.5.3 Assessments in GCF

GCF will be collected from 4 target sites at V2 and V3. The sampling should be performed before periodontal assessments. The selection of the target sites is described in section 7.3.5.2).

At the time of the analysis, in order to characterize the inflammatory response, immunoregulatory mediators in GCF  will be measured with two types of technologies, *i.e.*, bead-based multiplex assays (MAP) using the Luminex technology or targeted mass spectrometry.

Targeted mass spectrometry analysis will be performed using the quantitative parallel reaction monitoring (PRM) where the unique peptides of the selected protein targets will be analyzed for absolute quantitation in reference to a synthetic unique peptide of the selected protein

---

 sCD40L, CRP, EGF, Eotaxin/CCL11, Flt3 ligand, GM-CSF, GRO, IFN $\alpha$ 2IL-1 $\alpha$ , IL-1 $\beta$ , IL-1Ra, IL-2, IL-3, IL-4, IL-5, IL-6, IL-7, IL-8/CXCL8, IL-9, IL-10, IL-12 (p40), IL-12 (p70), IL-13, IL-15, IL-17A/CTLA8, IP-10/CXCL10, MCP-1/CCL2, MCP-3/CCL7, MDC/CCL22, MIP-1 $\alpha$ /CCL3, MIP-1 $\beta$ /CCL4, MMP-1, MMP-8, MMP-9, MMP-10, MMP-12, MMP-13, osteoprotegerin, PDGF-AA, PDGF-AB/BB, RANKL, RANTES/CCL5, TGF $\alpha$ , TIMP-1, TNF $\alpha$ , TNF $\beta$  / LT- $\alpha$  (please refer to the Abbreviations for full spelling)

### Confidentiality Statement

---

Data and information contained in this document are considered to constitute trade secrets and confidential commercial information, and the legal protections provided to such trade secrets and confidential information are hereby claimed under the applicable provisions of applicable law. No part of this document may be publicly disclosed without the written consent of Philip Morris Products S.A.

---

targets using mass spectrometry. Absolute quantitation will be performed using a heavy labeled synthetic peptide of the selected unique peptide of the target. The targets that will be analyzed by mass spectrometry are: MMP-8, MMP-12, MMP-13, CRP, RANKL, TIMP-1 and osteoprotegerin (please refer to the Abbreviations for full spelling).

#### 7.5.4 Assessments in Subgingival Plaque

SP will be collected from 4 target teeth, at V1 and V4 in order to evaluate the microbiological status. The sampling should be performed before periodontal assessments, except at V1, when it will be performed after periodontal assessments and designation of target teeth. If plaque sample is too small, additional collection can be performed on mesiobuccal SP of second molars, which needs to be recorded by the examiner. These teeth are the same than those selected for GCF collection (section 7.5.3). DNA isolation from these samples will enable the evaluation of the bacterial diversity and the detection of the abundance of bacteria in these samples. Some human host DNA (*i.e.*, of the patient) will also be isolated, however, the host DNA sequences obtained during the DNA sequencing will be filtered out of the raw sequencing data before analysis, and no formal analysis of the patient DNA will be performed.

#### 7.5.5 Assessments in Buccal Swabs

Buccal swabs will be derived from the right and left cheeks (intraoral) to conduct transcriptomics analysis at V2, V3 and V4. These samples will be analyzed for whole human genome expression profiles, also known as transcriptome. No analysis of the patient DNA will be performed.

#### 7.5.6 Sample Handling, Storage, and Shipment

The urine dip-stick for the urine pregnancy tests, and urine cotinine tests will be done by personnel at the study sites. Participating laboratories for the analyses of clinical samples are listed in Appendix 2. Detailed procedures for handling of samples are described in a separate Laboratory Manual / Sample Handling Manual (SHM). All samples that were planned for analysis will be destroyed post database lock or post finalization of the bioanalytical reports depending on which one is coming the latest.

#### 7.5.7 Self-reported Tobacco- or Nicotine-Containing Product Use

Patients will be questioned for their smoking history at V1. At V1, patients will also answer a questionnaire on self-reported current tobacco- and nicotine-containing product, with instructions from study staff so that they can then answer the questionnaire on their own on a monthly basis. After randomization, patients will be asked to complete a monthly diary, to record their self-reported tobacco- and nicotine- containing product consumption (including frequency and quantity of product use) over the past month. In this case, a “month” is to be

### Confidentiality Statement

---

Data and information contained in this document are considered to constitute trade secrets and confidential commercial information, and the legal protections provided to such trade secrets and confidential information are hereby claimed under the applicable provisions of applicable law. No part of this document may be publicly disclosed without the written consent of Philip Morris Products S.A.

---

considered as 30 days, however a “calendar month” window is acceptable. A flexibility of  $\pm 2$  day is allowed, whichever definition of the month is used. The sites will call the patients to remind them to fill the questionnaire. The Investigator or study collaborator will collect the completed diaries at V3 for Month 1 and Month 2 and for Month 3 only if the questionnaire completion date was before or on the day of the Visit. If the completion date of Month 3 questionnaire is after the V3 date, the Month 3 questionnaire will be brought to the next visit. All remaining questionnaires will be collected at V4, even if the 30-day period for completion of Month 6 questionnaire is after the date of V4. The diary data will be transcribed into the CRF by study staff.

## 7.6 Periodontal Treatment/Maintenance

For each patient, standard of care procedures as defined by the Japanese guideline on periodontal disease will be applied [78]. All medications/treatments provided to patients must be documented in source documentation. However, medication commonly used during SRP and maintenance treatment procedure will not be recorded as concomitant medication in the CRF, except if it is identified as causally related to an AE.

This section describes more specifically the mechanical treatment which is targeted for this study.

### 7.6.1 Scaling

Supragingival scaling will be performed at V1, and at further visits if required, including at unscheduled visits, based on PI’s judgement. Maintenance treatment will be provided in the order of supragingival scaling and plaque control at all other visits. Ultrasonic scaler usually used at each site will be used for scaling.

### 7.6.2 Scaling and Root Planing (SRP)

First SRP will be performed on teeth with PD  $\geq 4$  mm by using Gracey Hand Curettes at V2. The following SRP treatments will be performed and recorded as “unscheduled” SRP visits. SRP treatments of teeth with PD  $< 4$  mm will be performed based on PI’s judgment, at the time he/she finds it necessary. All SRP treatments must be completed within 8 weeks after V2. If additional SRP visits need to be performed because of periodontitis worsening, based on Investigator’s judgement, they will be recorded as unscheduled visits, including the reason for this unplanned SRP.

PD, mobility and BOP before SRP will be measured as per the standard of care treatments at V2. These data will, however, not be reported in the CRF.

The order of SRP should be determined for individual patients. The identification of each tooth treated and the respective time of treatment should be recorded.

## 8 ADVERSE EVENTS

A medically qualified monitor(s) (*i.e.*, medical monitor) will be available during the study to address any safety question an Investigator may have.

### 8.1 Definitions

#### 8.1.1 Adverse Events

According to ICH Topic E2A (Clinical Safety Data Management: Definitions and Standards for Expedited Reporting [98]), an AE is defined as any untoward medical occurrence in a patient administered an IP or reference product, which does not necessarily have a causal relationship with the IP or reference product. An AE can therefore be any unfavorable and unintended sign (including a clinically significant abnormal laboratory finding), symptom, or disease temporally associated with the use of an IP or reference product, whether or not it is considered related to the IP or reference product.

Any dental condition identified after signature of the ICF, caused by factors other than periodontitis (e.g. cavity, broken tooth) and requiring future treatment/s, will be identified as an AE. Treatment of this condition (e.g. cavity filling, tooth extraction) will be captured in the CRF.

Worsening of the periodontitis parameters after baseline assessments will not be considered as an AE, as dental assessments will capture any worsening of the periodontal condition. Patients experiencing unexpected worsening of the disease, will be treated based on Investigator's judgement, which will be recorded.

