### 8.2.2 Period of Collection

Any AEs (including SAEs) will be captured by the study site collaborators and assessed by the Investigator(s) or designee(s) in order to establish relationship to Investigational Products and study procedures. AEs will be collected from the time the patients have signed their ICFs until the end of the safety follow-up period.

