#### 8.2.2.1 Screening Visit (V1)

All existing health conditions identified during the screening visit and judged by the Investigator as preexisting condition will be recorded as concomitant disease and the patient's eligibility for admission to the study will be reviewed.

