#### **8.4 Reporting of other events critical to safety evaluations**

An ongoing medical condition, clinically relevant finding detected during the screening visit (V1), will be considered a concomitant disease and the patient's eligibility for participating to the study will be reviewed.

Any new, clinically relevant, abnormal finding or worsening of a pre-existing condition detected during the study after the screening visit until the end of the study will be documented as an AE.

Any new onset of symptoms or worsening of pre-existing symptoms identified through the study questionnaires may be documented as AEs at the discretion of the Investigator.

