### 9.1 Screening, Enrollment and Baseline Visit: V1

The screening, enrollment and baseline visit (V1) will be scheduled within 2 weeks (Day -14 to -7) prior to randomization visit (V2).

Patient will sign the study participation ICF before the start of any procedure, and will enter Screening. All eligibility criteria will be checked, including periodontal assessment, which will be also used as baseline assessment for enrolled patients.

Table 3 shows the assessments that will be performed at the screening, enrollment and baseline visit:

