8.4 Safety Set

The Safety Set consists of all patients enrolled with signed ICF who have at least one valid safety assessment during the course of the study. The Safety Set will be analyzed by actual exposure (see “product use pattern”).

Confidentiality Statement

Data and information contained in this document are considered to constitute trade secrets and confidential commercial information, and the legal protections provided to such trade secrets and confidential information are hereby claimed under the provisions of applicable law. No part of this document may be publicly disclosed without the written consent of Philip Morris Products S.A.

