Population	: 
 • Safety Sets 
 ➤ Product use pattern
Contents	: The number and percentage of patients experiencing concomitant disease and the number of concomitant disease will be counted by Medical Dictionary for Regulatory Activities (MedDRA, Version 20.0 or higher) SOC and PT. All cases collected on the form for concomitant disease (MHCAT=" CONCOMITANT DISEASE") will be tabulated.
Definition	: A concomitant disease is defined as any condition that started prior to ICF signature and is still ongoing at the end of V1.
Remark	: SOC and PT will be sorted by alphabetical order.
Output	15.2.3.2 Summary Table of Concomitant Disease - Safety Set -

Confidentiality Statement

Data and information contained in this document are considered to constitute trade secrets and confidential commercial information, and the legal protections provided to such trade secrets and confidential information are hereby claimed under the provisions of applicable law. No part of this document may be publicly disclosed without the written consent of Philip Morris Products S.A

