9.5.4 Safety Evaluation

9.5.4.1 Safety Reporting

9.5.4.2 Adverse Events

For AE tables, tabulations will be performed for both the number and percentage of patients experiencing an event and the number of events experienced during the study period by Medical Dictionary for Regulatory Activities (MedDRA, Version 20.0 or higher) System Organ Class (SOC) - sorted by alphabetical order, Preferred Terms (PT) - sorted by alphabetical order. If there is a change in severity for an AE for a subject, that event is counted once at the worst severity. If a subject has AEs that occurs and resolves on multiple occasions, each AE is counted once at the highest severity. Unless otherwise noted, target population will be used as denominator for frequency table.

Confidentiality Statement

Data and information contained in this document are considered to constitute trade secrets and confidential commercial information, and the legal protections provided to such trade secrets and confidential information are hereby claimed under the provisions of applicable law. No part of this document may be publicly disclosed without the written consent of Philip Morris Products S.A

All AEs will be summarized by product use group, SOC and PT. The adverse events that occurred during the study will be broken down and reported in the following ways,

- Occurrence of serious adverse events
- Severity of adverse events
- Relatedness of adverse event to study procedure and investigational product
- Adverse events leading to discontinuation

The tables below show the various ways in which adverse events will be reported for the study.

Summary Table of Adverse Events		
Population	:	
 • Safety Sets 
 ➤ Product use pattern
Contents	:	
The number and percentage of patients experiencing an adverse event and the number of adverse events during the study period.
 
The overview table 15.2.10.1 includes a summary of overall number of AEs, SAEs, severity and relation to study procedure or investigational product and response to adverse events.
 
The summary table 15.2.10.2 shows a tabulation of adverse events by SOC/PT.

Output		
15.2.10.1 Overview Table of Adverse Events - Safety Set -
 
15.2.10.2 Summary Table of Adverse Events - Safety Set -
 
15.3.10.1 Listing of Adverse Events - Safety Set -

Summary Table of Adverse Events by Severity		

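### A treatable non-periodontitis dental condition already present at V1 is both an adverse event (Protocol 8.1.1) and a concomitant disease (Protocol 7.3.4, 8.2.2.1, 8.4; SAP 9.3), and the SAP does not keep pre-product events out of the by-product AE tables

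*Protocol*

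**What the plan says.** Protocol 8.1.1 gives dental findings their own rule. An AE is "Any dental condition identified after signature of the ICF, caused by factors other than periodontitis (e.g. cavity, broken tooth) and requiring future treatment/s". What triggers it is the date of identification.

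Three other protocol sections and the SAP treat conditions found at screening differently:

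- Protocol 8.2.2.1: "All existing health conditions identified during the screening visit and judged by the Investigator as preexisting condition will be recorded as concomitant disease".
- Protocol 8.4: an ongoing condition or "clinically relevant finding detected during the screening visit (V1), will be considered a concomitant disease".
- SAP 9.3, using the same definition as Protocol 7.3.4: "A concomitant disease is defined as any condition that started prior to ICF signature and is still ongoing at the end of V1".

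Protocol 8.2.2.2 and 8.4 then make AEs of new findings, or worsening of existing ones, detected after the screening visit.

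On timing, Protocol 9.1 states: "Patient will sign the study participation ICF before the start of any procedure, and will enter Screening". Protocol 8.2.2 adds: "AEs will be collected from the time the patients have signed their ICFs until the end of the safety follow-up period". Allocated product starts at V2, 7 to 14 days after V1.

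On reporting, SAP 9.5.4.2 states: "All AEs will be summarized by product use group, SOC and PT". The tables use the Safety Set, which SAP 8.4 defines as "all patients enrolled with signed ICF who have at least one valid safety assessment during the course of the study" and groups by actual product use.

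**The concern.** AE incidence is a secondary endpoint, and Protocol 12.8 makes AE data the main assessment of safety. A cavity already present at V1 cannot be a consequence of switching to IQOS, because the device is not handed out until V2. If it is counted as an AE, it still appears under a product heading. If one site records such findings as AEs and another as concomitant disease, the sites' AE rates differ with no difference between their patients. In either case, a reader of the by-product tables cannot tell how much of a percentage arose after product use began.

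**Working it through.** The plan states no AE rate and no prevalence of cavities or broken teeth, so it has no figure to reproduce. The check is a cross-reading, followed by an illustration on assumed inputs.

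**Step 1: classify one finding.** Take a cavity that began before consent, is seen at the V1 examination and needs treatment.

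| Rule | What decides | Class |
|---|---|---|
| Protocol 8.1.1 | identified after consent, not periodontitis, needs treatment | AE |
| Protocol 7.3.4 and SAP 9.3 | began before consent, ongoing at end of V1 | concomitant disease |
| Protocol 8.2.2.1 | found at V1, Investigator judges it pre-existing | concomitant disease |
| Protocol 8.4 | clinically relevant finding at V1 | concomitant disease |

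Consent comes before every V1 procedure, so the 8.1.1 condition holds for anything seen at V1. All four rows apply at once, and no text gives one precedence.

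**Step 2: which rule would a site use?** Either is defensible. Section 8.1.1 is the dental-specific rule, and AE recording is scheduled at V1. Protocol Appendix 5 shows that its sentence was added in version 3.0 because sites were unsure what to record, and lists no matching change to 7.3.4, 8.2.2.1 or 8.4.

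**Step 3: does the SAP remove the event if it is recorded as an AE?** SAP 9.5.4.2 has no product-emergent or post-randomization restriction. The only date rule is in SAP 9.1.5.2:

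- partial date earlier than Screening: listings only;
- missing date, or partial date in or after the Screening month or year: summarized;
- complete date before Screening: no rule given.

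A cavity of unknown onset, dated V1 or left undated, is therefore tabulated.

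**Step 4: direction of the effect (all inputs assumed).** Let p be the true on-study AE incidence in a group and b the share of its patients with a V1 finding counted as an AE. If the two are independent, tabulated incidence = 1 − (1 − p)(1 − b). Take p = 20% in group A and 40% in group B.

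| b in A, b in B | A | B | B − A (points) | A/B |
|---|---|---|---|---|
| 0, 0 | 20% | 40% | 20 | 0.50 |
| 10%, 10% | 28% | 46% | 18 | 0.61 |
| 20%, 20% | 36% | 52% | 16 | 0.69 |
| 30%, 30% | 44% | 58% | 14 | 0.76 |
| 50%, 50% | 60% | 70% | 10 | 0.86 |
| 30%, 10% | 44% | 46% | 2 | 0.96 |
| 10%, 30% | 28% | 58% | 30 | 0.48 |

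For example, row six: 1 − 0.8 × 0.7 = 0.44 and 1 − 0.6 × 0.9 = 0.46. Equal b shrinks the difference. Unequal b can nearly erase it or widen it beyond the true 20 points.

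**The case against.** The best defence is that most of the text already gives the sensible answer. Protocol 7.3.4, 8.2.2.1 and 8.4 and SAP 9.3 all keep a pre-existing V1 finding out of the AE data, and 8.2.2.2 makes AEs of what is new or worse afterwards. A site reading these together may never record an old cavity as an AE. This stands: entry into the AE tables depends on which rule a site follows. A reader might infer that every AE from consent onward is tabulated. That goes too far, because SAP 9.1.5.2 sends AEs with a partial pre-Screening date to listings.

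The yield at V1 may also be small. The scheduled examination is periodontal, no caries assessment is listed, and known dental problems are taken in the history. This stands too, as a reason not to put a figure on the effect. It does not show that the yield is nil: inclusion criterion 5 foresees that some teeth will need extraction, without stating why.

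Finally, little of the output is exposed. AE results are counts and percentages with no planned test (Protocol 12.7). An old cavity would move the any-AE line, its severity category and its own organ-class and preferred-term rows. The product-related table should mostly escape, because Protocol 8.2.4 treats an event sufficiently explained by an underlying condition as not related. All of this limits the reach of the problem, but the two definitions still conflict.

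**Conclusion.** The contradiction holds: the same V1 finding satisfies both definitions, and the SAP has no general means of separating events that predate allocated product. Two consequences follow, each conditional. Where sites apply 8.1.1, pre-product dental conditions can enter the by-product AE incidence. Where sites differ, incidence varies for a definitional reason.

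A reader might go further and conclude that these findings dilute the group comparison toward no difference. The documents do not support that. It would require V1 findings to be equally common in every column, and the columns are formed by actual product use, so randomization does not secure that balance. The bias could run either way.

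Its size cannot be derived from the documents; the percentages in the illustration are assumptions and show direction only. The effect is confined to descriptive safety summaries. No test or error rate is touched, and the primary pocket depth analysis is unaffected. This is an inconsistency worth correcting because correction is cheap, not a threat to the trial's main conclusion.

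**What to change.** **Protocol 8.1.1.** Reconcile it with 7.3.4, 8.2.2.1, 8.2.2.2 and 8.4. Non-periodontitis dental conditions already present at the V1 examination are recorded as concomitant disease. Those newly detected or worsening after V1 are recorded as AEs. Events caused by V1 procedures remain AEs.

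**SAP 9.5.4.2.** Report AEs of any type, dental or not, with onset or detection before product allocation at V2 in a separate listing or pre-product column. Restrict the by-product incidence tables to AEs that start or worsen after that point. Because the onset of a cavity is often unknown, let the date of first detection decide when onset cannot be established. A cut at V1, or one limited to dental events, would leave the 7 to 14 days between V1 and V2, and other pre-product events, in the by-product tables.

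**Cost.** One date flag and one extra listing or column. Events already entered can be flagged from their recorded dates, so no new data collection is needed.
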